1.2. Collected On Both Veterans with SZ/SZA and their Family Members

1.2.1. Health Services Utilization. These will be gathered from two sources: 1) the electronic medical records of the VA and affiliated sites, and; 2) for outside providers a checklist that we have used in previous studies will collect simple counts of utilization and provider information, for which we will obtain a release of medical records from subjects and collect utilization data from each provider. Utilization will be treated as both an outcome measure and for behavioral health visits outside of the study as mediators of improvement.

1.2.2. Antipsychotic Medication Adherence. Medication adherence will be assessed using relatively standard methods that involve obtaining self-report information on medication adherence from a patient and their primary family caregiver. Patients are asked about the extent to which they took their medication as prescribed since the last interview, or at baseline, in the past 3-months, using a five point scale from "1) never missed taking my medication" to "5) I stopped taking the medication altogether." The primary family caregiver will also be asked the question about the patient. If there

is disagreement the accepted procedure is to take the lower of the two ratings as the patient's degree of adherence.

1.2.3. Social Support & Loneliness. The MOS Social Support Survey will be used to assess perceived and actual social support. It has excellent internal consistency (Cronbach's alpha from .90 to .97) and composite reliability (ranging from .93 to .97), and is relatively brief (19 items). The Revised UCLA Social Loneliness Scale will assess subjective feelings of loneliness and isolation. It has high internal consistency ($\alpha=.89\text{-.94}$), good test-retest reliability ($r=0.73$), and convergent and construct validity.

1.2.4. Perceived Stress. Perceived stress will be measured with the 14 item Perceived Stress Scale. The scale has good internal reliability ($\alpha=0.85$) and test-retest correlation ($r=0.85$).

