1.2.10. Treatment Satisfaction. The Client Satisfaction Questionnaire (CSQ-8) will be used to assess satisfaction with treatment. The CSQ-8 is used worldwide to assess client/patient satisfaction with services. It has good internal consistency (coefficient alpha 0.86 to 0.94) and concurrent validity.

1.2.11. Participant Treatment Exposure. We will log each subject's contact with treatment in each study arm. In the in-person arm this will include session attendance and any other contact with the therapists relevant to the treatment outside of the sessions. The same will be done for the DSW arm. This will also include any usage of the website, which will be logged on the server for each participant.

1.1.12. Intervention Initiation: DSW and in-person MFG. Treatment initiation will be defined as those that consent to participate in the study and then begin treatment. For both treatments two components of initiation will be tracked. First, will be participating in the Joining Sessions, then will be participation in the PSSW.

1.1.13. Intervention Engagement: DSW and in-person MFG. We will assess the number of Veterans who become engaged in the two treatments. Based on established standards for defining therapeutic treatment engagement as returning for treatment after the intake or initial session, we have previously defined initial engagement in DSW as participating in the PSSW and then using DSW to participate in an on-line group forum (e.g., logging on to the website and posting a ‘new member’ introduction) and an educational activity (e.g., reading an article). For in-person MFG intervention engagement will also be participating in the PSSW and then attending a first in-person group meeting.

1.1.14. Intervention Attendance/Commitment: DSW and in-person MFG. The number of weeks that participants attend each treatment will be assessed. For DSW this is defined as logging on to the website for at least 15 minutes in a week. For in-person MFG meetings are every other week, so each attendance covers two weeks.

1.1.15. Intervention Drop-out: DSW and in-person MFG. We will track the number of participants who drop-out of treatment in both arms. We will track those who officially drop-out of the study, and those who indicate that they no longer wish to receive treatment, though they may not drop-out of the study.

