Hypotheses 1.3. When compared to in-person MFG, Veterans and family members receiving DSW will have higher treatment initiation, engagement, attendance, lower drop-out, and higher perceived social support.

1.7.2. Specific Aim 2

We will conduct exploratory analyses to identify Veteran and family characteristics that are associated with severity of psychiatric symptoms and caregiver burden across both treatment arms. Analyses will look for important moderators (e.g. baseline symptom level, distance from hospital, age, technology expertise) as well as mediators (e.g., in-person meeting attendance, amount of DSW usage).

These analyses will be completed by supplementing the mixed effect regressions with demographic (age, race education), pre-study computer experience, support (living situation) and clinical characteristics (symptom severity, severity of cognitive impairment) of subjects that affect the relationships between the treatment and outcomes. Analyses will be carried out across both arms and then for each arm separately. While it is possible to test the treatment X non-treatment moderators with interaction terms the number of subjects precludes analyses that include all factors and interactions.

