Mediating effects of the different intervention components and different patterns of attendance and engagement are likely to occur in this study and will also be identified with mixed effect regressions. To test for mediating effects we will compare the relationships between treatment and outcomes and these potential mediating variables and outcomes. We assume that exposure, i.e., increased numbers of in-person session attendance, or more usage of DSW, will lead to greater improvements. These will help us to identify whether it is the amount of time spent on the materials/in treatment, or the duration of time one is exposed to treatment. Those in DSW and in-person MFG could have up to 1 year exposure, but usage patterns will identify the actual period of time over which Veterans were actually exposed to MFG materials, and the amount of time they used those materials. Thus, though the duration is the same in both treatments, the actual amount of exposure is not necessarily the same in both. For these analyses with 80 subjects in a multivariable regression with treatment included the detectable R^2 difference of an additional variable is 0.06 with 3 added variables it is 0.09 and with as many as 8 additional variables (or degrees of freedom) the detectable difference in R^2 is 0.12 (alpha=0.05, power=80%). The usual rule of thumb is to include at most $n/(8-10)$ variables in a multivariable regression, thus the analyses will be limited to 8 variables including the treatment variable.

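### The Aim 2 mediation test, as written, uses neither the treatment-to-mediator path nor an indirect effect, and is not linked to Hypothesis 1.3

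*Combined protocol and SAP*

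**What the plan says.** Section 1.7.2 (Specific Aim 2) is labelled exploratory. It gives as examples "mediators (e.g., in-person meeting attendance, amount of DSW usage". It says that mediating effects of intervention components, attendance and engagement "will also be identified with mixed effect regressions". The method is then one sentence: "To test for mediating effects we will compare the relationships between treatment and outcomes and these potential mediating variables and outcomes".

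The power statement in the same section is for the gain in R-squared when variables are added to a regression that already contains treatment: 0.06, 0.09 and 0.12 for 1, 3 and 8 added variables, with 80 subjects, alpha 0.05 and 80% power.

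Three other places bear on the point:

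- Section 1.2.1 (Health Services Utilization) adds a further candidate: "Utilization will be treated as both an outcome measure and for behavioral health visits outside of the study as mediators of improvement".
- Hypothesis 1.3 in section 1.7.1 states that Veterans and family members "receiving DSW will have higher treatment initiation, engagement, attendance, lower drop-out, and higher perceived social support", compared with in-person MFG.
- Section 1.1.14 puts attendance in weeks for both arms. The website rule reads: "For DSW this is defined as logging on to the website for at least 15 minutes in a week". A group session in the other arm is converted to the same unit by this rule: "For in-person MFG meetings are every other week, so each attendance covers two weeks".

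**The concern.** A variable mediates a treatment effect only if treatment changes the variable (path a) and the variable affects outcome given treatment (path b). The null of no mediation is that a or b is zero. The two relationships in the Aim 2 sentence are treatment-outcome (path c, the total effect) and mediator-outcome (path b). Path a is not among them.

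A test built only on b, or on b and c, therefore has the wrong null. A candidate can be strongly prognostic and have the same distribution in both arms. Outside behavioral health visits are the clearest case, because no between-arm comparison of them is stated. Section 1.7.2 also runs analyses within each arm, where there is no treatment contrast and only a predictor-outcome association can be seen.

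Requiring a treatment-outcome effect first does not repair this. The trial is designed to show that DSW and MFG have equivalent outcomes (section 1.8), so path c may be near zero even where pathways exist. What is at stake is whether Aim 2 reports predictors as mechanisms, or passes over real mechanisms. No primary conclusion depends on it.

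**Working it through.** **1. The plan's own figure.** For an R-squared gain D from k added variables, with treatment already in the model: f2 = D / (1 − R2base − D), noncentrality = 80 × f2, degrees of freedom k and 80 − k − 2. The plan does not give R2base.

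- At an assumed R2base of 0.30, the detectable gains at 80% power are 0.064, 0.088 and 0.121, matching the stated 0.06, 0.09 and 0.12 after rounding.
- At R2base of 0 they are 0.091, 0.126 and 0.173.
- For one variable with D = 0.06: f2 = 0.06/0.64 = 0.094 gives power 77% at R2base 0.30, and f2 = 0.06/0.94 = 0.064 gives 61% at R2base 0.

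This is power for path b alone. Read as a mediation criterion, it is also the chance of flagging a candidate of that strength that treatment does not change.

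**2. Simulation of the possible criteria.** T is treatment (0/1), M = a·T + e1, and Y = b·M + c'·T + √(1 − b²)·e2, with standard normal errors. There are 40 subjects per arm (the plan's 80, equal split assumed) and two-sided 0.05 OLS tests. b = 0.245 corresponds to the plan's R-squared (0.245² = 0.06). All other path sizes are assumptions. Percentages of trials in which a mediator is declared:

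| Scenario | a | b | c' | b only | b and c | a and b |
|---|---|---|---|---|---|---|
| No mediation | 0 | 0.245 | 0 | 59 | 3 | 3 |
| No mediation | 0 | 0.3 | 0 | 77 | 4 | 4 |
| No mediation, direct effect | 0 | 0.3 | 0.5 | 77 | 46 | 4 |
| True mediation | 0.7 | 0.4 | 0 | 96 | 22 | 84 |
| True mediation, cancelled | 0.7 | 0.4 | −0.28 | 96 | 5 | 83 |

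With 42 and 47 subjects the pattern is the same: 63% and 82% false flags on b only in the first two rows, and 24% against 88% detection in the fourth.

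**3. Hand check of the fourth row.** The within-arm SD of M and of Y is 1, so the standard error of a difference in means is √(2/40) = 0.224. The total effect is 0.7 × 0.4 = 0.28, and 0.28/0.224 = 1.25, so its power is about 24%. Path a gives 0.7/0.224 = 3.13, so its power is about 88%. Multiplying each by the 96% for path b gives about 23% and 84%.

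**4. Where path a does appear in the plan.**

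| Candidate | Between-arm comparison stated? | Linked to Aim 2? |
|---|---|---|
| Attendance, engagement | Yes, Hypothesis 1.3 | No |
| Outside behavioral health visits | No | No |
| In-person sessions; DSW usage | Not meaningful: each exists in one arm only | No |

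**The case against.** The strongest objection is that the plan states no decision rule. It does not say that a significant b, or significant b and c, makes a variable a mediator, and every percentage above belongs to a rule supplied for the calculation. Section 1.7.2 also describes adding variables to regressions that contain treatment. An analyst could take the sentence to mean comparing the treatment coefficient with and without the mediator. In linear models fitted to the same data that change equals a × b, so path a is carried implicitly. A Sobel test of it in the same scenarios gives 0.4 to 1.1% false flags and about 72% detection. This stands as a possible intention. However, the sentence names two different relationships, not one coefficient under two models, and the power statement is for the added variable, so the reading has to be written down before it can be relied on.

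A reader might also infer three stronger things that the documents do not support:

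- *That the plan never examines whether treatment changes a mediator.* Hypothesis 1.3 compares the arms on attendance and engagement, which are main candidates. What is missing is the link to Aim 2.
- *That any prognostic variable could be declared a mediator.* Candidates are limited to intervention components, attendance, engagement, usage and outside visits. Baseline characteristics are treated separately.
- *That one procedure both over-declares and misses mediators.* High false labelling with no treatment effect needs the b-only rule, which detects the true mediator 96% of the time. Missing mediators needs the added treatment-outcome requirement, which gives only 3 to 4% false flags when there is no treatment effect. It gives 46% only with an assumed direct effect of 0.5 SD.

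**Conclusion.** The point holds in limited form. As written, the Aim 2 test specifies no treatment-to-mediator model and no indirect effect, and does not draw on Hypothesis 1.3. Taken literally, it cannot separate a predictor from a mediator.

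The size depends on the reading. With the mediator-outcome association as criterion, about 59% false labelling at R-squared 0.06, against about 3% for the joint test of both paths. With a treatment-outcome effect also required, about 22% detection against 84%. The first figure uses the plan's own R-squared and sample size, with the equal split and no other covariates assumed. The second rests on assumed paths a = 0.7 SD and b = 0.4. Both assume a single measurement of each variable and no confounding of mediator and outcome.

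Severity is minor: Aim 2 is exploratory, and neither the sample size nor the non-inferiority conclusions depend on it.

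**What to change.** Replace the mediation sentence in section 1.7.2 with:

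> For each candidate mediator measured on a common scale in both arms (weeks of attendance as defined in 1.1.14, engagement, outside behavioral health visits), we will estimate (a) the effect of treatment on the mediator, using the Hypothesis 1.3 comparison where available, and (b) the effect of the mediator on outcome with treatment in the model, and report the indirect effect a × b with a bootstrap 95% confidence interval. A significant treatment-outcome effect is not required. Variables related to outcome but not changed by treatment, and exposure measures that exist in one arm only, will be reported as predictors or within-arm exposure associations, not mediators.

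The cost is a change of SAP wording and one extra regression per candidate, on data already to be collected. The downside is that fewer variables will be labelled mediators. Randomization protects path a but not path b, so the indirect effect will still rest on the assumption of no mediator-outcome confounding. The report should say so.

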42 and 47 subjects per treatment arm respectively (n=89 total) represent the number of Veterans that need to complete their assigned interventions. We expect that the non-completion rate for the in-person MFG arm to be $\leq 33\%$ and DSW arm to be $\leq 10\%$. Given these estimates 70 in person MFG subjects will be enrolled and 47 DSW subjects, for a total of 117 to account for attrition and non-completers. Sample size calculations used PASS (2008, NCSS, LLC, Kaysville Utah.).

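### The Aim 2 detectable R-squared values (0.06, 0.09, 0.12) need an unstated base-model R-squared of about 0.30; with treatment alone in the base model they are about 0.09, 0.13 and 0.165

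*Combined protocol and SAP*

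**What the plan says.** The last paragraph of section 1.7.2 (Specific Aim 2) in the combined protocol and SAP sets out what the moderator and mediator regressions can detect. The setting is "For these analyses with 80 subjects in a multivariable regression with treatment included". For one variable, "the detectable R^2 difference of an additional variable is 0.06"; "with 3 added variables it is 0.09"; and for as many as 8 additional variables or degrees of freedom, "the detectable difference in R^2 is 0.12". The error rates are given as "alpha=0.05, power=80" (per cent).

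The next sentence applies a rule of thumb for the number of regressors and concludes that "the analyses will be limited to 8 variables including the treatment variable".

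The R-squared of the model before variables are added is not given, and no base variable other than treatment is named. Earlier in 1.7.2 the analyses are called exploratory. They are described as supplementing the mixed effect regressions with demographic, technology, support and clinical characteristics, including symptom severity and cognitive impairment.

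**The concern.** A detectable increment in R-squared depends on how much variance the base model already explains: the more it explains, the smaller the increment that can be detected. The three stated figures therefore carry a hidden input. If the base model is what the text describes, with treatment as its only named member, that input should be close to zero, because the trial hypothesises that the website arm does as well as or better than the in-person arm within a non-inferiority margin.

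These figures tell a reader what a null moderator or mediator result means. If they are too small for the model described, Aim 2 looks more sensitive than it is, and a null finding may be taken as ruling out associations that the study had only a moderate chance of detecting.

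**Working it through.** **Inputs from section 1.7.2.** n = 80; treatment in the base model (one base variable); alpha 0.05; power 80%; k = 1, 3 or 8 added variables; stated increments 0.06, 0.09, 0.12; cap of 8 variables including treatment, so at most 8 − 1 = 7 added.

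**Input not in the documents.** The base-model R-squared, R²b. I show a range from 0 to 0.30.

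**Formula.** F test of an R-squared increment Δ:
- effect size f² = Δ / (1 − R²b − Δ)
- noncentrality λ = n·f², with df1 = k and df2 = n − k − 2
- inverted: Δ = (1 − R²b)·f² / (1 + f²)

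**Step 1: effect size needed at n = 80 for 80% power.** This does not depend on R²b.

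| k | df2 | λ needed | f² = λ/80 | Δ at R²b = 0, f²/(1 + f²) |
|---|---|---|---|---|
| 1 | 77 | 8.05 | 0.1006 | 0.091 |
| 3 | 75 | 11.49 | 0.1436 | 0.126 |
| 7 | 71 | 15.81 | 0.1977 | 0.165 |
| 8 | 70 | 16.73 | 0.2092 | 0.173 |

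**Step 2: reproduce the plan's figures.** Since Δ scales with (1 − R²b), the base value implied by each stated figure is:
- 1 − 0.06/0.0914 = 0.34
- 1 − 0.09/0.1256 = 0.28
- 1 − 0.12/0.1730 = 0.31

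Allowing for rounding to two decimals, any R²b from about 0.29 to 0.32 gives all three. At 0.30 the increments are 0.7 × (0.0914, 0.1256, 0.1730) = 0.064, 0.088, 0.121. The stated values can therefore be obtained at 80 subjects, but only with R²b of about 0.30.

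**Step 3: other base values, n = 80.**

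| R²b | Δ: 1 added | 3 added | 7 added | 8 added | Power at 0.06 / 0.09 / 0.12 (1 / 3 / 8 added) |
|---|---|---|---|---|---|
| 0 | 0.091 | 0.126 | 0.165 | 0.173 | 61 / 62 / 58% |
| 0.10 | 0.082 | 0.113 | 0.149 | 0.156 | 66 / 68 / 64% |
| 0.20 | 0.073 | 0.100 | 0.132 | 0.138 | 71 / 74 / 71% |
| 0.30 | 0.064 | 0.088 | 0.116 | 0.121 | 77 / 81 / 80% |

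The sidedness of alpha is not stated. A one-sided reading makes sense only for a single added variable, and at R²b = 0 it gives about 0.07, still above 0.06.

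**Step 4: can treatment alone explain 30%?** With equal arms, R² = d²/(d² + 4), where d is the standardised arm difference, so d = 2·√(0.30/0.70) = 1.31. For comparison, section 1.8 pairs a ratio of 1.20 with a coefficient of variation of 0.3. If the arm means differed by that full margin, d = 0.20/0.3 = 0.67 and R² = 0.444/4.444 = 0.10. Even the largest ratio in Hypothesis 1.1, 1.47, paired by assumption with the largest coefficient of variation in section 1.8, 0.5, gives d = 0.94 and R² = 0.884/4.884 = 0.18. A range of 0 to 0.10 is therefore reasonable for treatment alone.

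**Step 5: the cap.** Eight added variables plus treatment make 9, one more than the plan allows. Each further base covariate removes another: with treatment and one covariate in the base model, 8 − 2 = 6 can be added.

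**The case against.** The strongest reply is that nothing has been miscalculated. The text says that treatment is included, not that it stands alone. Aim 2 supplements mixed regressions that already use baseline and follow-up data, and a baseline symptom score could well explain 30% of the variance in a later one. One round base value, 0.30, gives all three figures at the stated 80 subjects. This part stands: the documents do not prove an arithmetic error, and the figures are attainable under an assumption that someone may have made.

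It does not rescue the text as written. No base covariate is named. The natural sources of explained variance, such as baseline symptom level and cognitive impairment, appear in 1.7.2 among the characteristics to be examined or added. Any covariate placed in the base model also uses up the cap.

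On the cap, it can fairly be said that the plan writes of variables or degrees of freedom, so a multi-level factor could bring 7 added variables to 8 degrees of freedom. The text does not say this is what is meant. The difference is in any case small: 0.165 against 0.173 at base 0, and 0.116 against 0.121 at base 0.30.

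A reader might also infer that the calculation was run with the wrong number of subjects. With 117 subjects and a base R-squared of 0 the increments are 0.064, 0.088 and 0.121, and section 1.8 plans enrolment "for a total of 117 to account for attrition and non-completers". The documents do not support that inference. Section 1.7.2 states 80, nothing links 117 to this calculation, and 80 subjects with a base of 0.30 give the same rounded values.

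**Conclusion.** The stated increments are too favourable for the model that the plan describes. They rest on a base R-squared of about 0.30 that is not stated and that treatment alone cannot plausibly supply here. With treatment explaining 0 to 10%, the stated values are about 28-34% too small at base 0 (0.06/0.0914 = 0.66, 0.09/0.1256 = 0.72, 0.12/0.1730 = 0.69) and about 20-27% too small at base 0.10 (0.06/0.0823 = 0.73, 0.09/0.113 = 0.80, 0.12/0.1557 = 0.77).

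It would go too far to say that the real power is 60%. That holds only for a base R-squared near zero; at 0.30 the nominal 80% is roughly met. Separately, and with no assumption needed, the 8-variable scenario and the cap disagree on the count of variables.

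The calculation treats the analysis as an ordinary regression with one record per subject, as the plan's own figures appear to do. It does not represent the time terms and repeated measures of the mixed models. The point is minor: Aim 2 is exploratory, and these figures neither set the sample size nor bear on the primary non-inferiority tests.

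**What to change.** In section 1.7.2, restate the detectable increments for 80 subjects and a treatment-only base model as about 0.09 for 1 added variable, 0.13 for 3 and 0.165 for 7, the most that the cap allows.

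If base covariates explaining about 30% were assumed, the current values for 1 and 3 variables can stay, provided that the text names those covariates, gives that R-squared beside the values and counts the covariates against the cap of 8. The largest model must then be reduced to fit, and its figure recalculated. If the 8 refers to degrees of freedom rather than variables, say so.

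Either route costs a sentence or two. The first makes the stated sensitivity less favourable. Neither changes the design, the sample size or the primary analysis.
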